8.3.2.3 Non-Clinical Outcomes

- Change in FVIII treatment satisfaction and preference ratings from caregiver between ADVATE reconstituted in 5 mL and 2 mL SWFI
- Change in FVIII infusion volume and time to mix and infuse FVIII treatment between ADVATE reconstituted in 5 mL and 2 mL SWFI

8.4 Randomization and Blinding

This is a non-randomized, open-label, non-interventional PASS study.

8.5 Study Stopping Rules

Stopping rules will not be established for this non-interventional PASS study since all treatment regimens will be prescribed at the discretion of the investigators according to the product marketing authorization.

8.6 Study Product

8.6.1 Packaging, Labeling, and Storage

Each ADVATE pack contains a powder vial, a 2 mL solvent vial (both type I glass closed with chlorobutyl rubber stoppers) and a device for reconstitution (BAXJECT II).

ADVATE has a shelf life of 2 years when stored in a refrigerator ($2^{\circ}C - 8^{\circ}C$). Do not freeze. During the shelf life, the product may be kept at room temperature (up to $25^{\circ}C$) for a single period not exceeding 6 months. Please record the beginning of storage at room temperature on the product carton. The product may not be returned to refrigerated storage after storage at room temperature. Keep the vial in the outer carton in order to protect from light.

After reconstitution, ADVATE should be administered at room temperature within 3 hours. From a microbiological viewpoint, the product should be used immediately after reconstitution.

8.6.2 Administration

ADVATE should be administered via the i.v. route. The solution should be administered slowly at a rate as determined by the patient's comfort level, not to exceed 10 mL/minute.

8.6.3 Description of Treatment

The treatment regimen, dosing and duration of treatment are at the discretion of the treating physician.

For subject's ≤ 2 years of age, use of the 250 IU size vials is recommended.

Information on treatment is provided in the SmPC as follows:

The posology and duration of the substitution therapy depend on the severity of the FVIII deficiency, on the location and extent of the bleeding and on the patient's clinical condition.

The dose of FVIII is expressed in International Units (IU), which are related to the WHO standard for FVIII products. FVIII activity in plasma is expressed either as a percentage (relative to normal human plasma) or in IUs (relative to the international standard for FVIII in plasma).

One IU of FVIII activity is equivalent to that quantity of FVIII in one mL of normal human plasma. The calculation of the required dose of FVIII is based on the empirical finding that 1 IU FVIII per kg body weight (BW) raises the plasma FVIII activity by 2 IU/dL. The dose is determined using the following formula:

Required units (IU) = BW (kg) x desired FVIII rise (%) x 0.5

In case of the following hemorrhagic events, the FVIII activity should not fall below the given plasma activity level (in % of normal or IU/dL) in the corresponding period. The following table (Table 8.6-1) can be used to guide dosing in bleeding episodes and surgery:

Table 8.6-1 Guide for Dosing in Bleeding Episodes and Surgery			
Degree of Hemorrhage / Type of Surgical Procedure	FVIII Level Required (% or IU/dL)	Frequency of Doses (Hours) / Duration of Therapy (Days)	
Hemorrhage			
Early hemarthrosis, muscle bleeding or oral bleeding.	20 – 40	Repeat injections every 12 to 24 hours (8 to 24 hours for patients under the age of 6) for at least 1 day, until the bleeding episode, as indicated by pain, is resolved or healing is achieved.	
More extensive hemarthrosis, muscle bleeding or hematoma.	30 – 60	Repeat injections every 12 to 24 hours (8 to 24 hours for patients under the age of 6) for 3 – 4 days or more until pain and acute disability are resolved.	
Life threatening hemorrhages.	60 – 100	Repeat injections every 8 to 24 hours (6 to 12 hours for patients under the age of 6) until threat is resolved.	
Surgery			
Minor Including tooth extraction.	30 – 60	Every 24 hours (12 to 24 hours for patients under the age of 6), at least 1 day, until healing is achieved.	
Major	80 – 100 (pre- and postoperative)	Repeat injections every 8 to 24 hours (6 to 24 hours for patients under the age of 6) until adequate wound healing, then continue therapy for at least another 7 days to maintain a FVIII activity of 30% to 60% (IU/dL).	

The dose and frequency of administration should be adapted to the clinical response in the individual case. Under certain circumstances (eg, presence of a low-titre inhibitor), doses larger than those calculated using the formula may be necessary.

During the course of treatment, appropriate determination of plasma FVIII levels is advised to guide the dose to be administered and the frequency of repeated injections. In the case of major surgical interventions in particular, precise monitoring of the substitution therapy by means of plasma FVIII activity assay is indispensable. Individual patients may vary in their response to FVIII, achieving different levels of *in vivo* recovery and demonstrating different half-lives.

For long-term prophylaxis against bleeding in patients with severe hemophilia A, the usual doses are 20 to 40 IU of FVIII per kg BW at intervals of 2 to 3 days. In patients under the age of 6, doses of 20 to 50 IU of FVIII per kg BW 3 to 4 times weekly are recommended.

8.6.4 Study Product Accountability

Commercially available ADVATE will be used in this open-label, non-interventional, PASS study. No study product accountability will be employed. All exposure will be captured in subject diaries provided to the subjects (or routinely kept by the subjects) and clinical records routinely kept at the study site and will be transposed to the study case report forms (CRFs).

9. SUBJECT SELECTION, WITHDRAWAL, AND DISCONTINUATION

9.1 Inclusion Criteria

Subjects who meet ALL of the following criteria are eligible for this study:

- Subject has severe or moderately severe hemophilia A (baseline FVIII ≤ 2%)
- Subject is ≤ 12 years of age
- Subject's legally authorized representative(s) has provided written informed consent
- Subject is prescribed ADVATE and will only receive ADVATE reconstituted in 2 mL SWFI
- Documented history of prior exposure to ADVATE (for subjects ≤ 2 years old, at least 3 EDs to ADVATE; for subjects with ≤ 50 EDs, all prior EDs must be to ADVATE; for subjects with >50 EDs, the last 20 prior EDs must be to ADVATE)
- Documented evidence of negative inhibitor test result during ≤10 EDs prior to study entry

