6.3 Population to Be Studied

The study population will include 60 evaluable subjects aged \leq 12 years with severe or moderately severe hemophilia A (FVIII \leq 2%) with documented prior exposure to FVIII concentrates. Thirty (30) subjects will be \leq 6 years and the remaining 30 subjects will be \geq 6 to \leq 12 years of age. Of the 30 subjects \leq 6 years of age, at least 15 subjects will be \leq 2 years old. Ongoing enrollment will carefully be monitored to help ensure that the study population reflects the age categories specified.

The targeted enrollment will be 73 subjects. This number was determined to offset the projected dropout rate of 17% experienced in the ADVATE previously untreated patient (PUP) study (060103)^{iii,7}, and to ensure that there are 60 evaluable subjects.

The patient population to be studied (pediatric patients, aged \leq 12 years) is of an age that the participants are not able to provide informed consent. However, appropriate consent procedures will be in place, and the consent of the patient's legally authorized representative(s) will be obtained.

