6.5.2 Inhibitor Development

The formation of neutralizing antibodies (inhibitors) against FVIII is a known complication in the management of individuals with hemophilia A. These inhibitors are usually IgGs directed against the FVIII procoagulant activity, which are quantified in BU per mL of plasma using the modified Bethesda assay. In patients who develop inhibitors to FVIII, the condition may manifest itself as an insufficient clinical response. In such cases, it is recommended that a specialized hemophilia centre be contacted. The risk of developing inhibitors is correlated to the extent of exposure to FVIII, the risk being highest within the first 20 EDs, and to other genetic and environmental factors. Rarely, inhibitors may develop after the first 100 EDs. Cases of recurrent inhibitor (low titer) have been observed after switching from one FVIII product to another in previously

treated patients with more than 100 EDs who have a history of inhibitor development. Patients treated with coagulation FVIII should be carefully monitored for the development of inhibitors by appropriate clinical observations and laboratory tests.

The formation of inhibitors to FVIII is a known complication in the management of patients with hemophilia A. The risk of developing inhibitors correlates to the extent of prior exposure to FVIII, with the risk being highest within the first 20 EDs. *De novo* inhibitor formation is less commonly observed after 100 EDs.

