11.4 Clinical Laboratory Parameters

11.4.1 FVIII Inhibitor Titer

Documentation of a negative inhibitor test during ≤10 EDs before initiation of ADVATE reconstituted in 2 mL SWFI is an inclusion criterion. Thereafter, the investigators shall determine the frequency for inhibitor testing based on routine screening schedule, as appropriate within respective countries and subject to relevant clinical guidelines, or clinical signs. It is recommended that inhibitor testing is performed in the presence of clinical signs suggesting inhibitor development: increased bleeding tendency, high consumption, lack of response or efficacy, decreased IR, shortened half life. If an inhibitor is suspected, it is also recommended to look at FVIII IR. If the IR appears greatly reduced and/or no FVIII is detected, an inhibitor is suspected. It should be kept in mind that the normal PK range may be age-related, with children exhibiting different kinetics (shorter half-life and lower IR) compared to adults.

The inhibitor assay methods and reference standard used will be reported in the CRF. In the case a positive inhibitor titer is detected, a confirmatory test on a second, separately drawn sample should be performed. This second sample should be taken prior to any change of treatment and shortly (within 1 month) after the previous positive test. Results of FVIII IR and half-life tests should be recorded with associated washout period, FVIII dose administered and sampling times. All laboratory testing will be done at the local lab.

Negative inhibitor titer: any titer below the limit of inhibitor detection of the local lab; if local lab reference value is not available, any titer <0.6 BU by the Nijmegen modification Bethesda assay, or < 1 BU by a non-Nijmegen modification Bethesda assay.

Low-titer inhibitor titer: any titer higher than the limit of inhibitor detection of the local lab and ≤ 5 BU; if local lab reference value is not available, any titer ≥ 0.6 BU by the Nijmegen modification Bethesda assay, or ≥ 1 BU by a non-Nijmegen modification Bethesda assay.

High-titer inhibitor titer: any titer > 5 BU at any time after diagnosis.

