21. SUPPLEMENTS

21.1 Schedule of Study Procedures and Assessments

Table 21.1-1
Schedule of Study Procedures and Assessments

Procedures/Assessments	Screening Visit	Interval Study Visits	Study Completion/ Termination Visit ^a	
Informed Consent ^b	X			
Eligibility Criteria	X			
Medical History	X	X	X	
Medications	X	X	X	
Physical Exam	X	X	X	
Surgical or Dental Procedures		X	X	
Subject Diary	X	X	X	
Adverse Events		X	X	
Laboratory Tests ^c	X	X	X	
Vital Signs	X	X	X	
Satisfaction/preference caregiver survey ^d	X		X	

Includes cases of withdrawal or discontinuation.

b. Occurs at enrollment (before screening).

No non-routine laboratory tests are mandated by this protocol; laboratory data that has been collected through routine practice should be recorded in the CRFs.

d. This survey is strictly optional and will only be offered where such a survey is in concordance with non-interventional study regulations and after EC approval of its use.

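### For children who enter with few exposure days, the 10-ED window for the negative inhibitor test can cover most or all of their prior FVIII exposure, so an inhibitor formed before entry could be counted as on-study

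*Protocol*

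**What the plan says.** Protocol section 9.1 (repeated in the synopsis) makes one inhibitor test a condition of entry: "Documented evidence of negative inhibitor test result during ≤10 EDs prior to study entry". The criterion just before it sets the exposure required: "for subjects ≤ 2 years old, at least 3 EDs to ADVATE" and "for subjects with ≤ 50 EDs, all prior EDs must be to ADVATE". For children older than 2 with 50 or fewer EDs no minimum number is given; section 9.2 excludes only those with no FVIII exposure at all.

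Section 11.4.1 restates the test with a different anchor: "Documentation of a negative inhibitor test during ≤10 EDs before initiation of ADVATE reconstituted in 2 mL SWFI is an inclusion criterion". After entry, the investigator decides when to test. Section 10.3.1 lists an inhibitor titer at entry among the screening data, but eligibility does not depend on it, and the footnote to Table 21.1-1 says "No non-routine laboratory tests are mandated by this protocol". Section 10.7 says the same in other words.

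Section 6.3 plans a stratum of very young children: within the younger half of the 60 evaluable subjects, "at least 15 subjects will be" aged 2 or under. Section 6.5.2 describes inhibitor risk in terms of cumulative exposure, "the risk being highest within the first 20 EDs". Section 14.4.2 counts inhibitors in the whole safety analysis set and, separately, in two sets of previously treated patients with more than 50 EDs and no inhibitor history.

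**The concern.** A look-back of 10 EDs is short for a child with hundreds of EDs and long for a child with three. The window is a fixed number of EDs, whereas the risk it screens for is concentrated in the first few. In the children with least exposure, the qualifying negative result may say little or nothing about their status after exposure to FVIII.

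Nothing else in the protocol closes this. Among the exclusion criteria, only ongoing immune tolerance induction bears on a current inhibitor. The entry titer is a data item and no test is mandated to fill it, so the value recorded may be the old qualifying test. Section 14.4.2 has no rule for an inhibitor that may have been present at entry.

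At stake is the all-subjects inhibitor count, a secondary safety outcome. A child who formed an inhibitor before entry and is first tested afterwards could add a case to it, which would bias the count for the 2 mL product upward. Section 11.1.1 also makes every inhibitor a serious adverse event. The sponsor's own study in previously untreated patients was stricter: in its risk-factor analysis (section 6.4.1), children without an inhibitor were included only once they had 10 or more EDs.

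**Working it through.** **Inputs.** Window 10 EDs (9.1, 11.4.1). Minimum exposure 3 EDs at age 2 or under; none stated for older children with 50 or fewer (9.1). High-risk period 20 EDs (6.5.2). Planned children aged 2 or under: at least 15 of 60, i.e. 15/60 = 25% (6.3). Inhibitors in the previously untreated patient study: 16/55 (6.4.1).

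**The plan's own figures.** 16/55 = 29.1%; the normal-approximation 95% interval is 0.291 ± 1.96 × √(0.291 × 0.709/55) = 17.1% to 41.1%, as printed. Target enrollment 60/(1 − 0.17) = 72.3, rounded up to 73, also as printed. Neither is in dispute.

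**How much exposure the qualifying test can miss.** Take a child with k EDs at entry.

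- Permissive reading (a sample before the first infusion is allowed): the earliest qualifying sample is at ED max(0, k − 10), so the unchecked share is min(k, 10)/k.
- Strict reading (the word *during* requires at least one prior ED): the earliest sample is after ED max(1, k − 10), so the unchecked share is min(k − 1, 10)/k.

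| EDs at entry | Unchecked, permissive | Unchecked, strict |
|---|---|---|
| 3 | 3/3 = 100% | 2/3 = 67% |
| 5 | 5/5 = 100% | 4/5 = 80% |
| 10 | 10/10 = 100% | 9/10 = 90% |
| 11 | 10/11 = 91% | 10/11 = 91% |
| 15 | 10/15 = 67% | 10/15 = 67% |
| 20 | 10/20 = 50% | 10/20 = 50% |
| 50 | 10/50 = 20% | 10/50 = 20% |

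The two readings differ only at 10 EDs or fewer. Even the strict one leaves two thirds or more of prior exposure unchecked from 3 to 15 EDs.

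**The restricted sets.** With at least 51 EDs, the earliest qualifying sample is at ED 51 − 10 = 41, well past the first 20.

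**Possible size (assumptions, not in the documents).** Let m children enter with 10 or fewer EDs and only an uninformative test, and let a share s of the 29.1% risk have materialized by entry. Expected cases = m × s × 16/55; chance of at least one = 1 − (1 − s × 16/55)^m.

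| m | s | Expected cases | Chance of at least one |
|---|---|---|---|
| 3 | 0.10 | 0.09 | 8.5% |
| 5 | 0.25 | 0.36 | 31% |
| 10 | 0.25 | 0.73 | 53% |
| 15 | 0.25 | 1.09 | 68% |
| 15 | 0.50 | 2.18 | 90% |

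**The case against.** The case for leaving the criterion alone has real content.

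- **Wording.** A reader might infer that a sample drawn before any FVIII plainly qualifies. The text does not settle this: *during* can be read as requiring some exposure. That stands, but the strict column above shows it only narrows the gap.
- **Entry titer.** A reader might infer that a pre-existing inhibitor will be counted as a 2 mL inhibitor. It only could be. Section 10.3.1 lists the entry titer as its own item, and where it is actually measured an existing inhibitor would show. Because no test is mandated, this reduces the gap without closing it.
- **Product.** Prior ADVATE need not mean the 5 mL presentation. Section 9.1 names no volume, and section 10.3.1 records the current 2 mL regimen and its start date at screening. An inhibitor from pre-entry EDs on 2 mL would not be misattributed to that product. This stands, and it is why the two anchors matter.
- **Reach.** The outcome is secondary and descriptive, each inhibitor has an individual causality assessment (11.1.4), and the protocol nowhere states that the criterion is meant to establish onset on 2 mL. All true. The all-subjects count is still reported without separating such cases.
- **Size.** At the 3 to 4 weekly infusions that section 8.6.3 gives for under-sixes, 10 EDs take 10/4 = 2.5 to 10/3 = 3.3 weeks, so many children on prophylaxis may enter above 10 EDs. In the previously untreated patient study all inhibitors arose at FVIII below 1%, and 0/20 children lacking all three risk factors developed one. The upper end of the range is therefore a stacked worst case.
- **Remedy.** Demanding a sample after the most recent ED would amount to a mandated entry test, in tension with a non-interventional design. This stands and shapes the fix.

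**Conclusion.** The concern holds as a limited design gap. The window can span most of the prior exposure of children who enter with few EDs and, on a permissive reading, all of it. This falls in the period the protocol itself regards as highest risk. An inhibitor formed before entry could therefore enter the all-subjects count, and any bias would be upward.

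The size cannot be fixed from the documents, which give no ED distribution at entry. About 0.1 to 2 expected cases covers 3 to 15 affected children and 10% to 50% of a 29.1% risk arising before entry. The upper end assumes that all 15 planned children aged 2 or under qualify on an uninformative test. One or two such cases should not be taken as the expected result, although even one would be visible among 60 evaluable children.

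Nor should a reader conclude that the immunogenicity results as a whole are compromised: the two sets restricted to more than 50 EDs are not open to the pre-exposure problem. Conversely, the gap is not confined to age 2 or under, since an older child with few EDs is in the same position.

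**What to change.** 1. **Outcome rule (14.4.2).** Keep the all-subjects count as it is. For subjects with 20 or fewer total EDs at entry, report a first positive titer on a separate line, labelled as onset before study entry or 2 mL not excluded, unless the last negative sample followed the last ED before the 2 mL product. Section 10.3.1 already lists what this mainly needs: the exact ED count for subjects with 50 or fewer, the 2 mL regimen start date and the entry titer. The cut-off follows the protocol's own high-risk period. If the analysis plan already contains such a rule, a cross-reference is enough.
2. **Eligibility wording (9.1, synopsis, 11.4.1).** State that the qualifying negative sample must follow prior FVIII exposure. This removes the permissive reading.
3. **Anchor.** Use one start point for the window in all three places. Section 9.1 and the synopsis count back from study entry and 11.4.1 from the start of 2 mL; these differ for a child already on 2 mL at screening.

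Do not mandate an additional test. The cost is a sentence in each place and one reporting rule. The downside is small: a few cases move to a separate line, and a child whose only negative sample predates all exposure would need a later routine result to qualify.

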9.2 Exclusion Criteria

Subjects who meet **ANY** of the following criteria are not eligible for this study:

- Subject has known hypersensitivity to the active substance or to any of the excipients
- Subject has a known allergic reaction to mouse or hamster proteins
- Subject has a requirement for a major surgical procedure at the time of enrollment
- Subject has no prior exposure to a FVIII concentrate
- Subject is currently being treated with an immune tolerance induction (ITI) regimen
- Subject has been diagnosed with an inherited or acquired hemostatic defect other than hemophilia A (eg, qualitative platelet defect or von Willebrand disease)
- Subject has participated in another clinical study involving an investigational product (IP) or investigational device within 30 days prior to enrollment or is scheduled to participate in another clinical study involving an IP or investigational device or PASS registry during the course of this study

9.3 Withdrawal and Discontinuation

Any subject may voluntarily withdraw consent for continued participation and data collection. The reason for withdrawal will be recorded on the CRF Completion/Discontinuation page. Assessments to be performed at the termination visit (including in cases of withdrawal or discontinuation) are described in Section 10.6 and Section 21.1. The data collected on withdrawn subjects will be used in the analysis and included in the clinical study report.

Discontinuation (ie, complete withdrawal from study participation) may be due to dropout (ie, active discontinuation by subject) or loss to follow-up (ie, discontinuation by subject without notice or action).

Subjects will be withdrawn from further study participation if a subject develops a low-titer inhibitor and can no longer be adequately managed with ADVATE reconstituted in 2 mL SWFI or if a subject develops a high-titer inhibitor.

10. STUDY PROCEDURES

10.1 Informed Consent and Enrollment

Any patient whose legally authorized representative(s) provides informed consent (ie, legally authorized representative(s) signs and dates the ICF and patient signs and dates assent form, if applicable) is considered enrolled in the study.

10.2 Subject Identification Code

The following series of numbers will comprise the subject identification code (SIC): protocol identifier (eg, 061101) to be provided by the sponsor, 2-digit number study site number (eg, 02) to be provided by the sponsor, and 4-digit subject number (eg, 0003) reflecting the order of enrollment (ie, signing the ICF). For example, the third subject who signed an ICF at study site 02 will be identified as Subject 061101-020003. All study documents (eg, CRFs, clinical documentation, etc.) will be identified with the SIC. Additionally, a uniquely coded SIC(s) is permitted as long as it does not contain a combination of information that allows identification of a subject (eg, collection of a subject's initials and birth date would not be permitted), in compliance with laws governing data privacy.

